2.0 STUDY OBJECTIVES

2.1 Primary Objective

To characterize the changes in immune gene signature (IGS) expression in blood and tumor samples after treatment with pembrolizumab alone compared to the combination of pembrolizumab and entinostat.

Hypothesis: We hypothesize that class I HDAC inhibition with entinostat added to pembrolizumab will increase T cell immune gene signature expression compared with pembrolizumab alone.

2.2 Secondary Objectives

- 2.2.1 To characterize the changes in neoantigen expression and T cell receptor (TCR) clonality in blood and tumor samples after treatment with pembrolizumab alone and the combination of pembrolizumab and entinostat.
- 2.2.2 To evaluate the changes in STAT and NF-κB gene signatures and histone acetylation (H3K9Ac, H3K27Ac, and others) levels after combination treatment with pembrolizumab and entinostat as compared to pembrolizumab alone (subset of subjects with frozen pre- and post-treatment tumor tissue available).
- 2.2.3 To document safety, tolerability, and feasibility of preoperative administration of pembrolizumab with and without entinostat in cisplatin-ineligible MIBC patients prior to scheduled surgical resection, and to document safety, tolerability and feasibility of pembrolizumab with and without entinostat prior to trimodality therapy in MIBC patients (National Cancer Institute Common Terminology for Adverse Events [NCI-CTCAE v5.0]).
- 2.2.4 To define the pathologic response rate (<pT2) and pathologic complete response rate (pT0) after treatment with pembrolizumab alone and the combination of pembrolizumab and entinostat in cisplatin-ineligible subjects undergoing radical cystectomy
- 2.2.5 To estimate the clinical complete response rate (cT0) after treatment with pembrolizumab alone and the combination of pembrolizumab and entinostat in patients undergoing maximal TURBT prior to chemoradiation
- 2.2.6 To estimate the event free survival (EFS) after treatment with pembrolizumab alone and the combination of pembrolizumab and entinostat in patients with MIBC

- 2.2.7 To estimate overall survival (OS) after treatment with pembrolizumab alone and the combination of pembrolizumab and entinostat in patients with MIBC
- 2.3 Exploratory Objectives

3.0 STUDY ENDPOINTS

3.1 Primary Endpoint

Change in immune gene signature expression will be defined based on change in the T cell immune gene signature from mRNAseq analysis in the pembrolizumab + entinostat group compared to the pembrolizumab alone group

3.2 Secondary Endpoints

- **3.2.1** Pre- and post-treatment TCR repertoire and neoantigen changes will be defined by changes in TCR clonality and neoantigen load.
- 3.2.2 Pre- and post-treatment changes in STAT and NF-κB expression will be evaluated using mRNAseq analysis and changes in histone acetylation (H3K9Ac and H3K27Ac) levels in a subset of subjects with pre- and post-treatment tumor tissue available (diagnostic TURBT and maximal TURBT or cystectomy tissue available)
- 3.2.3 Toxicity will be evaluated according to guidelines from National Cancer Institute

 Common Terminology for Adverse Events (NCI-CTCAE) criteria version 5.0
 and include all adverse events continuing or occurring 30 days after completion of treatment
- **3.2.4** A pathologic response will be defined as <pT2 (pT0-T1N0M0) and pathologic complete response will be defined as pT0N0M0 at the time of cystectomy at the completion of study treatment.
- 3.2.5 The clinical complete response rate (cT0) is defined as cT0 at the time of maximal TURBT
- **3.2.6** EFS is defined as day 1 of neoadjuvant/protocol treatment to date of first documentation of disease progression (or until recurrence after surgery or radiation) or death due to any cause. Recurrence includes the development of second primary muscle-invasive urothelial malignancies.
- **3.2.7** Overall survival is defined as day 1 of neoadjuvant/protocol treatment to date of death due to any cause. Patients will be censored at date of last follow-up.

3.3 Exploratory Endpoints

4.0 **SUBJECT ELIGIBILITY**

In order to participate in this study a subject must meet all of the eligibility criteria outlined below.

4.1 Inclusion Criteria

- **4.1.1** Written informed consent obtained to participate in the study and HIPAA authorization for release of personal health information.
- 4.1.2 Subjects must agree to donate tumor tissue from their diagnostic transurethral resection of the bladder tumor (TURBT) and from their post-treatment surgery (cystectomy or repeat maximal TURBT). Subjects must also agree to donate whole blood prior to initiating therapy, during study therapy and at post-treatment surgery.
- **4.1.3** Age \geq 18 years at the time of consent.
- **4.1.4** Eastern Cooperative Oncology Group performance status of ≤ 2 .
- **4.1.5** Histological confirmation of urothelial carcinoma of the bladder; those with mixed histology, including a component of urothelial carcinoma, are eligible. Pure small cell carcinoma, pure adenocarcinoma, and pure squamous cell carcinoma are excluded.
- **4.1.6** Subject has clinical stage T2-T4a N0/X M0 urothelial carcinoma. Clinical T stage is based on the pre-study standard of care transurethral resection of the bladder tumor (TURBT) sample and imaging studies (abdominal/pelvic CT or MRI scan and CT scan of the chest performed within 4 weeks prior to treatment initiation).
- **4.1.7** Available formalin-fixed paraffin-embedded (FFPE) archival tumor specimen that contains sufficient tissue to generate at least 15 (preferably 20) unstained slides, each with tissue sections that are 5 10 microns thick.
- **4.1.8** Subject is planned to undergo definitive therapy for MIBC with either surgery (radical cystectomy) or trimodality therapy (including repeat TURBT followed by concurrent chemoradiation). Subjects undergoing trimodality therapy must be deemed to not be a candidate for radical cystectomy, or refuse radical cystectomy. Suggested chemotherapy regimens are outlined in Appendix E but not mandated by protocol.
- **4.1.9** Subject demonstrates adequate organ function as defined in the table below; all screening laboratory assessments should be performed within 10 days of treatment initiation.

System	Laboratory Value
--------	------------------

Hematological	
Absolute neutrophil count (ANC)	$\geq 1.5 \times 10^{9}/L$
Platelets	≥100 × 10 ⁹ /L
Hemoglobin	≥9 g/dL
Renal	
Estimated GFR per CKD-EPI equation	≥30 mL/min
Hepatic	
Serum total bilirubin	≤ 1.5 mg/dL (subjects with Gilbert's syndrome may be enrolled despite a total bilirubin level >1.5 mg/dL if their conjugated bilirubin is <1.5 × ULN)
AST (SGOT) and ALT (SGPT)	\leq 2.5 \times ULN
Coagulation	
International normalized ratio (INR) OR prothrombin time (PT)	≤1.5 × ULN unless participant is receiving anticoagulant therapy as long as PT or aPTT is within therapeutic range of intended use of anticoagulants

- **4.1.10** If subject is planned to undergo radical cystectomy, subject refuses to receive or is ineligible to receive cisplatin-based neoadjuvant chemotherapy. Determination of ineligibility for cisplatin is based on at least one of the following criteria:
 - Eastern Cooperative Oncology Group performance status of 2
 - GFR per CKD-EPI equation ≤ 60 mL/min
 - NCI CTCAE version 5.0 Grade ≥ 2 hearing loss
 - NCI CTCAE version 5.0 Grade ≥ 2 neuropathy
- **4.1.11** Female subjects of childbearing potential should have a negative serum pregnancy within 72 hours prior to receiving the first dose of the study treatment. Non-childbearing potential is defined as (by other than medical reasons):
 - \geq 45 years of age and has not had menses for \geq 2 years
 - amenorrheic for <2 years without a hysterectomy and oophorectomy and a follicle-stimulating hormone value in the postmenopausal range upon pre-study (screening) evaluation
 - post hysterectomy, oophorectomy or tubal ligation.
- **4.1.12** Female subjects of childbearing potential must be willing to use an adequate method of contraception as outlined in Appendix D, for the course of the study through 120 days after the last dose of study medication.

Note: Abstinence is acceptable if this is the usual lifestyle and preferred contraception for the subject.

4.1.13 Male subjects of childbearing potential must agree to use an adequate method of contraception as outlined in Appendix D, starting with the first dose of study therapy through 120 days after the last dose of study therapy.

Note: Abstinence is acceptable if this is the usual lifestyle and preferred contraception for the subject.

- **4.1.14** Subject is able to tolerate and retain oral medication.
- **4.1.15** Life expectancy greater than 3 months.

4.2 Exclusion Criteria

The subject must be excluded from participating in the trial if the subject meets any of the following:

- **4.2.1** Subject is currently participating in or has participated in a study of an investigational agent or using an investigational device within 4 weeks of the first dose of pembrolizumab.
- **4.2.2** Subject has a diagnosis of immunodeficiency or is receiving systemic steroid therapy or any other form of immunosuppressive therapy within 7 days prior to the first dose of trial treatment. Inhaled and topical steroids are allowed.
- **4.2.3** Subject has a known history of active tuberculosis.
- **4.2.4** Subject has known hypersensitivity to pembrolizumab or any of its excipients.
- **4.2.5** For subjects in arm 2 only: Subject has allergy to benzamide or inactive ingredients of entinostat.
- **4.2.6** Subject has a known additional malignancy that is progressing or requires active treatment. Exceptions include basal cell carcinoma of the skin, squamous cell carcinoma of the skin, or *in situ* cervical cancer that has undergone potentially curative therapy.
- 4.2.7 Subject has active autoimmune disease that has required systemic treatment in the past 2 years (i.e. with use of disease modifying agents, corticosteroids or immunosuppressive drugs). Replacement therapy (e.g., thyroxine, insulin, or physiologic corticosteroid replacement therapy for adrenal or pituitary insufficiency, etc.) is not considered a form of systemic treatment.
- **4.2.8** Subject has a history of (non-infectious) pneumonitis/interstitial lung disease that required steroids or a current pneumonitis/interstitial lung disease.
- **4.2.9** Subject has an active infection requiring systemic therapy.

- **4.2.10** Subject has a history or current evidence of any condition, therapy, or laboratory abnormality that might confound the results of the trial, interfere with the subject's participation for the full duration of the protocol treatment, or is not in the best interest of the subject to participate, in the opinion of the treating investigator. Please note that subjects with Grade ≥2 peripheral neuropathy, are allowed on this study in addition to subjects with Grade <2 peripheral neuropathy.
- **4.2.11** Subject has known psychiatric or substance abuse disorders that would interfere with cooperation with the requirements of the trial.
- **4.2.12** Subject is pregnant or breastfeeding or expecting to conceive or father children within the projected duration of the trial, starting with the pre-screening or screening visit through 120 days after the last dose of trial treatment.
- **4.2.13** Subject has received prior therapy with an anti-PD-1, anti-PD-L1, anti-PD-L2, anti-CD137, or anti-cytotoxic T-lymphocyte-associated antigen-4 (CTLA-4) antibody (including ipilimumab or any other antibody or drug specifically targeting T-cell co-stimulation or checkpoint pathways).
- **4.2.14** Subject has had prior systemic cytotoxic chemotherapy for urothelial carcinoma (prior intravesicular chemotherapies are permitted).
- **4.2.15** Subject is receiving histone deacetylase inhibitors, including valproic acid, DNA methyltransferase inhibitors.
- **4.2.16** For subjects in arm 2 only: Subject is receiving drugs that are known to inhibit or induce P-gp (see Appendix B).
- **4.2.17** For subjects in arm 2 only: Subject has gastrointestinal impairment that may significantly affect absorption of entinostat, such as ulcerative disease, malabsorption syndrome, and a history of small bowel resection.
- **4.2.18** Subject has received prior radiation therapy to the bladder for the purpose of treating urothelial carcinoma.
- **4.2.19** Subject has a known history of Human Immunodeficiency Virus (HIV) (HIV 1/2 antibodies).
- **4.2.20** Has a known history of Hepatitis B (defined as Hepatitis B surface antigen [HBsAg] reactive) or known active Hepatitis C virus (defined as HCV RNA [qualitative] is detected) infection. Note: no testing for Hepatitis B and Hepatitis C is required unless mandated by local health authority.

- **4.2.21** Subject has received a live vaccine or live-attenuated vaccine within 30 days prior to the first dose of study drug. Administration of killed vaccines is allowed.
- **4.2.22** For subjects in arm 2 only: Subject uses drugs or herbal supplements that are known sensitive CYP substrates of CYP1A2, CYP2C8, CYP3A with narrow therapeutic range (see Appendix B).

5.0 TREATMENT PLAN

5.1 Schema

[figure not shown]

Figure 2. Translational sample collection schema

5.2 Treatment Dosage and Administration

After screening and enrollment, blood and archived diagnostic TURBT tumor tissue will be collected from each subject for baseline analyses. Subjects will then be administered pembrolizumab 200 mg IV alone on day 1 and day 22 (Arm 1) or entinostat 5 mg PO followed by pembrolizumab 200 mg IV on day 1, entinostat 5 mg PO on days 8 and 15, and pembrolizumab 200 mg IV on day 22 (Arm 2). Blood and tumor will then be collected from each subject at the time of post-treatment surgery (cystectomy or maximal TURBT).

Agent	Precautions	Dose	Route	Schedule ³
Pembrolizumab ²	Risk for immune-mediated and infusion-related ¹ reactions	200 mg	IV; administer over 30 min (range -5, +10 min)	Administer on Day 1 and Day 22

Entinostat ²	Take on an empty stomach i.e., at least 2 hours after a meal and at least 1 hour before the next meal.	5 mg	Oral (PO)	Administer on Days 1, 8 and 15
-------------------------	--	------	-----------	--------------------------------------

- 1. See Section 5.7.1 for management guidelines for infusion-related AEs
- 2. Entinostat should be taken before the pembrolizumab infusion.
- 3. Allowed window for administration of both pembrolizumab and entinostat is ± 1 day

5.3 Treatment Arm Assignment

Patients will be assigned to Arm 1 or 2. The allocation preference is to Arm 2 first, then Arm 1.

5.4 Toxicities and Dosing Delays/Dose Modifications

Any subject who receives a dose of entinostat and/or pembrolizumab on this protocol will be evaluable for toxicity. Each subject will be assessed periodically for development of any toxicity according to the Time and Events table. Toxicity will be assessed according to the NCI-CTCAE version 5.0.

AEs associated with pembrolizumab exposure, including coadministration with additional compounds, may represent an immunologic etiology. These immune-related AEs (irAEs) may occur shortly after the first dose or several months after the last dose of pembrolizumab/combination treatment and may affect more than one body system simultaneously. Therefore, early recognition and initiation of treatment is critical to reduce complications. Based on existing clinical study data, most irAEs were reversible and could be managed with interruptions of pembrolizumab/combination treatment, administration of corticosteroids and/or other supportive care. For suspected irAEs, ensure adequate evaluation to confirm etiology or exclude other causes. Additional procedures or tests such as bronchoscopy, endoscopy, skin biopsy may be included as part of the evaluation. Based on the severity of irAEs, withhold or permanently discontinue pembrolizumab and administer corticosteroids. Dose modification and toxicity management guidelines for irAEs associated with pembrolizumab/combination treatment are provided in the table below.

Attribution of Toxicity:

When study interventions are administered in combination, attribution of an adverse event to a single component is likely to be difficult. Therefore, while the investigator may attribute a toxicity event to the combination, to entinostat alone, or to pembrolizumab alone, for adverse events listed in the table below, both interventions must be held according to the criteria in the table.

Holding Study Interventions:

When study interventions are administered in combination, if the AE is considered immune-related, both interventions should be held according to recommended dose modifications.

Restarting Study Interventions:

Participants may not have any dose modifications (no change in dose or schedule) of pembrolizumab in this study, as described in the table below

- If the toxicity does not resolve or the criteria for resuming treatment are not met, the participant must be discontinued from all study interventions.
- If the toxicities do resolve and conditions are aligned with what is defined
 in the table below, the combination of entinostat and pembrolizumab may
 be restarted at the discretion of the investigator. In these cases where the
 toxicity is attributed to the combination or to entinostat alone, re-initiation
 of pembrolizumab as a monotherapy may be considered at the principal
 investigator's discretion.

Dose modification and toxicity management guidelines for immune-related AEs associated with pembrolizumab monotherapy and IO Combinations

General instructions:

- 1. Severe and life-threatening irAEs should be treated with IV corticosteroids followed by oral steroids. Other immunosuppressive treatment should begin if the irAEs are not controlled by corticosteroids.
- 2. Study intervention must be permanently discontinued if the irAE does not resolve or the corticosteroid dose is not ≤10 mg/day within 12 weeks of the last study intervention treatment.
- 3. The corticosteroid taper should begin when the irAE is ≤ Grade 1 and continue at least 4 weeks.
- 4. If study intervention has been withheld, study intervention may resume after the irAE decreased to

 ≤ Grade 1 after corticosteroid taper.

irAEs	Toxicity Grade (CTCAE v5.0)	Action With Pembrolizum ab	Corticosteroid and/or Other Therapies	Monitoring and Follow-up
	Grade 2	Withhold	Administer corticosteroids (initial dose of 1 to 2 mg/kg prednisone or	Monitor participants for signs and
Pneumonitis	Recurrent Grade 2, Grade 3 or 4	Permanently discontinue	equivalent) followed by taper Add prophylactic antibiotics for opportunistic infections	symptoms of pneumonitis • Evaluate participants with suspected pneumonitis with radiographic imaging and initiate corticosteroid treatment

	Grade 2 or 3 Recurrent	Withhold Permanently	Administer corticosteroids (initial dose of 1 to 2 mg/kg prednisone or equivalent) followed by taper	Monitor participants for signs and symptoms of enterocolitis (ie, diarrhea, abdominal)
	Grade 3 or Grade 4	discontinue		pain, blood or mucus in stool with or without fever) and of bowel perforation (ie, peritoneal signs and ileus) • Participants with ≥Grade 2 diarrhea suspecting colitis
Diarrhea/Coli tis				should consider GI consultation and performing endoscopy to rule out colitis
				Participants with diarrhea/colitis should be advised to drink liberal quantities of clear fluids. If sufficient oral fluid intake is not feasible, fluid and electrolytes should be substituted via IV
				substituted via IV infusion

AST or ALT Elevation or Increased Bilirubin	Grade 3 b or 4 c	Withhold Permanently discontinue	Administer corticosteroids (initial dose of 0.5 to 1 mg/kg prednisone or equivalent) followed by taper Administer corticosteroids (initial dose of 1 to 2 mg/kg prednisone or equivalent) followed by taper	Monitor with liver function tests (consider weekly or more frequently until liver enzyme value returned to baseline or is stable)
T1DM or Hyperglycem ia	New onset T1DM or Grade 3 or 4 hyperglyce mia associated with evidence of β-cell failure	Withhold ^d	Initiate insulin replacement therapy for participants with T1DM Administer antihyperglycemic in participants with hyperglycemia	Monitor participants for hyperglycemia or other signs and symptoms of diabetes
	Grade 2	Withhold	Administer corticosteroids and initiate hormonal replacements as	Monitor for signs and symptoms of
Hypophysitis	Grade 3 or 4	Withhold or permanently discontinue ^d	clinically indicated	hypophysitis (including hypopituitarism and adrenal insufficiency)
Hyperthyroidi	Grade 2	Continue	Treat with nonselective beta-blockers (eg, propranolol) or thionamides as	Monitor for signs and symptoms of
sm	Grade 3 or 4	Withhold or permanently discontinue d	appropriate	thyroid disorders
Hypothyroidi sm	Grade 2, 3 or 4	Continue	Initiate thyroid replacement hormones (eg, levothyroxine or liothyronine) per standard of care	Monitor for signs and symptoms of thyroid disorders
Nephritis: grading	Grade 2	Withhold	Administer corticosteroids	Monitor changes of
according to increased creatinine or acute kidney injury	Grade 3 or 4	Permanently discontinue	(prednisone 1 to 2 mg/kg or equivalent) followed by taper	renal function

Neurological Toxicities	Grade 2 Grade 3 or 4	Withhold Permanently discontinue	Based on severity of AE administer corticosteroids	Ensure adequate evaluation to confirm etiology and/or exclude other causes
Myocarditis	Grade 1 Grade 2, 3 or 4	Withhold Permanently discontinue	Based on severity of AE administer corticosteroids	Ensure adequate evaluation to confirm etiology and/or exclude other causes
Exfoliative Dermatologic Conditions	Suspected SJS, TEN, or DRESS Confirmed SJS, TEN, or DRESS	Withhold Permanently discontinue	Based on severity of AE administer corticosteroids	Ensure adequate evaluation to confirm etiology or exclude other causes
All Other irAEs	Persistent Grade 2 Grade 3	Withhold or discontinue based on the event e	Based on severity of AE administer corticosteroids	Ensure adequate evaluation to confirm etiology or exclude other
	Recurrent Grade 3 or Grade 4	Permanently discontinue		causes

AE(s)=adverse event(s); ALT= alanine aminotransferase; AST=aspartate aminotransferase; CTCAE=Common Terminology Criteria for Adverse Events; DRESS=Drug Rash with Eosinophilia and Systemic Symptom; GI=gastrointestinal; IO=immuno-oncology; ir=immune related; IV=intravenous; SJS=Stevens-Johnson Syndrome; T1DM=type 1 diabetes mellitus; TEN=Toxic Epidermal Necrolysis; ULN=upper limit of normal.

Note: Non-irAE will be managed as appropriate, following clinical practice recommendations.

- a AST/ALT: >3.0 to 5.0 x ULN if baseline normal; >3.0 to 5.0 x baseline, if baseline abnormal; bilirubin:>1.5 to 3.0 x ULN if baseline normal; >1.5 to 3.0 x baseline if baseline abnormal
- b AST/ALT: >5.0 to 20.0 x ULN, if baseline normal; >5.0 to 20.0 x baseline, if baseline abnormal; bilirubin:>3.0 to 10.0 x ULN if baseline normal; >3.0 to 10.0 x baseline if baseline abnormal
- c AST/ALT: >20.0 x ULN, if baseline normal; >20.0 x baseline, if baseline abnormal; bilirubin: >10.0 x ULN if baseline normal; >10.0 x baseline if baseline abnormal
- d The decision to withhold or permanently discontinue pembrolizumab is at the discretion of the investigator or treating physician. If control achieved or ≤ Grade 2, pembrolizumab may be resumed.
- e Events that require discontinuation include, but are not limited to: encephalitis and other clinically important irAEs.

Management of toxicities that are at least possibly related to entinostat, with toxicities graded by the Investigator according to the NCI CTCAE version 5.0 should be managed as follows:

Toxicity	Dose Modifications for Entinostat						
	Non-hematologic Toxicity						
Grade ≥ 3	Administer symptomatic remedies/start prophylaxis. Hold dose until recovery to Grade 1 or baseline under the following directions: If not recovered to Grade ≤ 2 within 1 week, permanently discontinue study drug.						
Grade ≤ 2	Administer symptomatic remedies/start prophylaxis.						
	Hematologic Toxicity						
Grade ≥ 3 neutropenia, Grade ≥ 3 uncomplicated thrombocytopenia, or Grade 2 complicated thrombocytopenia	Administer symptomatic remedies/start prophylaxis. Hold dose until recovery to Grade 1 or study baseline. If not recovered by next scheduled dose, skip the dose. If recovered by next scheduled dose, resume study drug at prior dose.						

Entinostat may also be held for grade 2 treatment-related adverse events if deemed necessary by the site investigator. If treatment is held due to an adverse event clearly attributable to entinostat that is not listed in the table above and not immune-related, then the pembrolizumab may be continued (i.e. monotherapy). If the event is clearly attributable to pembrolizumab, then both agents will be held. If it is not possible to determine attribution, then both agents will be held. If more than one dose hold for the same event occurs, then the attributable drug should be permanently discontinued (ie, if entinostat is held twice for the same treatment-related adverse event, it will be permanently discontinued, but pembrolizumab may be continued). Doses of either drug should not be delayed, and any held doses will not be made up.

All protocol treatment will be permanently discontinued for any grade 4 non-hematologic event. Permanent discontinuation of all protocol related treatment will also occur for grade 3 non-hematologic adverse events such as myocardial infarction, poorly controlled arrhythmias, and adverse events requiring significant surgical intervention for management. Additionally, if grade >2 drug-related toxicity occurs that does not respond to supportive care within 48 hours and does not resolve to grade ≤ 1 within this timeframe, then the subject will be withdrawn from all protocol treatment and followed until symptom resolution.

Additionally, all protocol treatment will be permanently discontinued if patients have clinical disease progression or development of metastatic disease or require treatment with high dose steroids beyond 2 weeks.

Dose modifications/dose adjustments of either pembrolizumab or entinostat are not allowed.

Safety stopping rules for drug-related toxicity will dictate whether the trial should be halted if 2 subjects have their cystectomy (or maximal TURBT) delayed beyond the 10 weeks from the time of initiation of study therapy due to drug toxicity.

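### Section 5.4 gives conflicting stopping instructions for the same adverse event and does not say which rule takes precedence

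*Combined protocol and SAP*

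**What the plan says.** All the text at issue is in protocol section 5.4.

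- **Grade 4 sentence** (after the entinostat table): "All protocol treatment will be permanently discontinued for any grade 4 non-hematologic event". It has no exceptions.
- **48-hour rule** (same paragraph): a drug-related toxicity above grade 2 that "does not respond to supportive care within 48 hours and does not resolve to grade ≤ 1 within this timeframe" leads to withdrawal from all protocol treatment. It is not limited to non-hematologic or non-immune events.
- **irAE table, hypothyroidism row**: for grades 2, 3 and 4 the pembrolizumab action is Continue, with the instruction "Initiate thyroid replacement hormones (eg, levothyroxine or liothyronine) per standard of care".
- **irAE table, footnote d** (type 1 diabetes or hyperglycemia, hypophysitis, hyperthyroidism): withholding or permanently stopping is left to the treating physician, and "If control achieved or ≤ Grade 2, pembrolizumab may be resumed".
- **irAE table, diarrhea/colitis row**: a first grade 3 event is Withhold. The cells run together in the extracted text ("Grade 2 or 3 Recurrent"); we read them as Withhold for grade 2 or 3, and permanent discontinuation for recurrent grade 3 or grade 4.
- **Entinostat table, non-hematologic grade 3 or higher**: hold until recovery, then "If not recovered to Grade ≤ 2 within 1 week, permanently discontinue study drug".
- **Entinostat table, grade 3 or higher neutropenia or thrombocytopenia**: "Hold dose until recovery to Grade 1 or study baseline. If not recovered by next scheduled dose, skip the dose". If the event has recovered by then, dosing resumes at the prior dose.
- **Attribution paragraph**: "for adverse events listed in the table below, both interventions must be held according to the criteria in the table". It does not mention the grade 4 or 48-hour rules.

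**The concern.** The grade 4 and 48-hour rules sit beside two tables that cover many of the same events with different actions and time limits. The trial is now multicentre. Section 11.5 requires it to be run exactly as the approved protocol describes, so where the rules collide a site that obeys one departs from the other. At stake is whether a subject receives treatment that another sentence says must stop, or loses treatment that a table says to continue. The treatment actually received in arms of 10 could then depend on which paragraph a site reads.

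**Working it through.** The plan gives no figure to reproduce here. The check sets the rules side by side, compares the time limits and counts the doses affected.

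**1. Grade 4 sentence (stop everything permanently) against each row that covers grade 4**

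| Row | Action in the table | With the grade 4 sentence |
|---|---|---|
| Hypothyroidism | Continue | Cannot both be followed |
| Entinostat, non-hematologic, grade 3 or higher | Hold; discontinue only if not grade 2 or lower at 1 week | Cannot both be followed |
| Hyperglycemia with beta-cell failure | Withhold, footnote d | Can both be followed; discretion and resumption lost |
| Hypophysitis | Withhold or permanently discontinue, footnote d | Same |
| Hyperthyroidism | Withhold or permanently discontinue, footnote d | Same |
| Pneumonitis, colitis, liver, nephritis, neurological, myocarditis, other irAEs | Permanently discontinue | Agree |

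This gives 2 rows in conflict and 3 that lose discretion. The hyperglycemia row itself says only Withhold. If footnote d is not read as permitting permanent discontinuation there, the split is 3 and 2.

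**2. 48-hour rule against the time limits in the tables**

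- Entinostat non-hematologic row: 1 week = 7 × 24 = 168 hours, and 168 / 48 = 3.5 times longer. A grade 3 event that has not responded at 48 hours but reaches grade 2 on its fifth day is withdrawn under one rule and not discontinued under the other.
- Entinostat hematologic row: hold, skip or resume, with no withdrawal. Neutropenia that has not responded at 48 hours but recovers by the next weekly dose is withdrawn under one rule and resumes under the other.
- irAE table: a first grade 3 diarrhea/colitis is Withhold. The general limit for irAE resolution is 12 weeks = 12 × 7 × 24 = 2016 hours, and 2016 / 48 = 42 times longer.

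That makes three places with a different action for the same event.

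**3. Doses affected**

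Section 5.2 leaves one dose after day 1 in Arm 1 (pembrolizumab, day 22) and three in Arm 2 (entinostat, days 8 and 15; pembrolizumab, day 22).

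- *Arm 2, entinostat-related grade 3 neutropenia on day 8, no response and not grade 1 or lower by day 8 + 2 = day 10, grade 1 by day 15.* The day 8 dose is held under either rule. The 48-hour rule also removes days 15 and 22. The hematologic row resumes on day 15 and does not stop day 22. Two of the three later doses differ.
- *Grade 4 hypothyroidism before day 22, either arm.* The day 22 pembrolizumab dose is given under the table and not under the grade 4 sentence.
- *Steroid-treated irAE.* A taper of at least 4 weeks starting no earlier than day 1 cannot end before day 1 + 28 = day 29. The last dosing day is 22 + 1 = day 23 at the latest, and held doses are not made up. No pembrolizumab dose differs, only whether the subject is recorded as held or withdrawn.

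**4. Search for a precedence rule**

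The grade 4 and 48-hour paragraph adds rules without ranking them against the tables. The attribution paragraph concerns which drug to hold. The provision on events clearly due to entinostat says only when pembrolizumab may go on alone. Section 5.8 refers back to itself for its criteria, and section 5.11 lists only unacceptable adverse events. None of these settles the order.

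**The case against.** The strongest reply has four parts.

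- **Most cases resolve on a natural reading.** The grade 4 and 48-hour sentences come after both tables, are worded absolutely and look like added stopping criteria. Most grade 4 irAE rows already agree with them. But that order is not written down, and adopting it would make the Continue entry void at grade 4 and cancel footnote d at that grade.
- **The entinostat non-hematologic row is a soft conflict.** It never says to resume, so stopping early arguably breaches nothing in it. It is indeed less stark than the hypothyroidism and hematologic rows. Still, it orders a hold until recovery, discontinues only after 1 week, and refers to the study drug, not all protocol treatment.
- **The irAE table is headed as guidelines, and the attribution paragraph only prevents holding one drug alone.** That paragraph does use must, and nothing in it makes the table give way to the later sentences.
- **The dose-changing cases are narrow.** Hematology is scheduled on days 1, 8, 15 and 22, so a day 10 count is unscheduled. The thyroid panel is scheduled only at screening and pre-surgery, so grade 4 hypothyroidism before day 22 would have to present clinically. This stands as a limit on frequency, although the 48-hour rule itself calls for an assessment at 48 hours. An event that is improving at 48 hours may also escape that rule, because its two conditions are joined by and.

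**Conclusion.** The concern holds and must be fixed. As written, section 5.4 gives incompatible actions for the same event. The clearest cases are grade 4 hypothyroidism, and grade 3 or higher neutropenia or thrombocytopenia that has not responded at 48 hours. In total, two rows conflict with the grade 4 sentence (three on the stricter reading of hyperglycemia), three lose discretion (two on that reading), and three places differ from the 48-hour rule.

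The effect is at subject level: up to two of the three remaining Arm 2 doses in the neutropenia example, and one pembrolizumab dose in the hypothyroidism example. One such subject is 1/10 = 10% of an arm. The documents give no basis for estimating how often these events would arise here, and they may be few. The consequence for the results is limited: anyone dosed stays evaluable for toxicity (sections 5.4 and 8.4), and subjects who stop early but have surgery are still asked for samples (section 8.2). The case for correction rests on safety and on sites being able to follow the protocol, not on power.

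**What to change.** Reconcile the irAE table with its footnotes, the entinostat table, and the grade 4 and 48-hour sentences in section 5.4, so that each event and grade leads to one action. State for each action whether it covers one drug or all protocol treatment. Add one sentence saying which rule takes precedence where they overlap. Which rule should apply is for the clinical team and the safety committee to decide; this review takes no position on it.

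The cost is a protocol wording amendment. Sample size, visits and data collection do not change.
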